The investigator examines the subject's lesion(s) and makes the clinical assessment of the subject lesion(s) based on established clinical decision algorithms (such as "Chaos & clues", "3- or 7-point checklist", or the ABCDE concept) of whether there is a suspicion of MM, according to the usual clinical routine (also includes very low suspicion of MM but cannot be completely dismissed). The investigator takes dermoscopy images according to standard of care and archives the image(s) according to clinical routine. The investigator decides on action, based on his or her MM suspicion (excision at the primary care centre or referral for excision or referral to a dermatologist for further

Template Doc. id. Version

02

Document	Doc. id.	Version	Page	
Clinical investigation Plan / Investigation code- AI-DSMM/	GR 21- 023	01	11 (52)	_

assessment). If the subject has agreed to participate in the investigation, the investigator indicates in the CRF the clinical suspicion level of MM, and decided action.

The investigator takes images of the lesion(s) again, this time with a mobile phone, containing the IMD AI SW, connected to a dermatoscope, and follows the on-screen instructions. The image is processed by the AI SW and the results are visible on the screen within seconds. A unique auto generated code number is also presented. The code number is registered on the enrollment log and in the CRF. The investigator records how he considers that the degree of suspicion of MM (higher vs lower) would have been affected by the AI SW result if it had been the governing body for the treatment.

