When the subject has been fully examined and receives the final tumor diagnosis from the histopathology/PAD results (melanoma/non melanoma), the degree of agreement between the PAD and the outcome of the AI SW decision support is calculated with the Kappa-analysis and the diagnostic accuracy to be able to distinguish melanoma from non-melanoma in the form of sensitivity and specificity as well the positive and predictive value. The corresponding comparison is performed from the examining investigators' estimated clinical degree of suspicion, as well as the diagnostic accuracy when both the PAD and the AI decision support are weighted together (i.e. in cases where the investigator and the decision support are in agreement in their assessment). The clinical investigation will collect information from the users, how participating users (investigators at the site) experience the usability of the AI SW decision support and attaching applications, from short surveys including the validated System Usability Scale.

Use the same overall description given in Section 9.1.

Duration of exposure to the Investigational Medical Device

The subjects will not be in any direct contact with IMD Dermalyzer.

Duration of subjects' involvement in the investigation

The subjects will only perform 1 visit at a primary care centre to assess the cutaneous lesion(s).

Clinical performance assessments

The subject will be examined according to clinical routine. The cutaneous lesions where MM cannot be ruled out (study lesions) will be photographed with a digital dermatoscope. The digital image will then be able to be instantly uploaded to the study's AI enhanced web application (Dermalyzer), where the AI algorithm performs the image analysis within a few seconds.

Template Doc. id. Version

02

CIP Template QMS 12-01-

Document	Doc. id.	Version	Page
Clinical investigation Plan / Investigation code- AI-DSMM/	GR 21- 023	01	12 (52)

Clinical safety assessments

All considered reportable events in accordance with MDR, will be captured. The subject included in the investigation will follow the standard of care. The use of the AI will not influence the subject or the medical care of the subject.

Statistical methods

The sample size of at least eligible 239 lesions is calculated by an expected true proportion of 95% with 80% power. The estimated frequency of actual found malignant melanoma is 4.65% (or 12 MM out of 239 lesions).

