9 INVESTIGATIONAL PLAN

9.1 Overall investigational design and schedule of events

The subjects will be included from primary care centres. If the subject's lesion(s) is suspected of melanoma or melanoma cannot be ruled out the subject is asked to participate in the investigation. The investigator examines the subject's lesion(s) (with or without a dermatoscope) and may also take dermoscopy images according to standard of care. The investigator then makes his clinical

Document	Doc. id.	Version	Page	
Clinical investigation Plan / Investigation code- AI-DSMM/	GR 21- 023	01	23 (52)	_

assessment of the subject lesion(s) based on established clinical decision algorithms (such as "Chaos and clues", "3- or 7-point checklist", or the ABCDE criteria) of whether there is a suspicion of melanoma, according to the usual clinical routine (also includes very low suspicion that cannot be completely dismissed). The investigator decides on action based on his or her MM suspicion (excision at the primary care centre or referral for excision or referral to a dermatologist for further assessment), see figure 1.

If the subject has agreed to participate in the investigation, the investigator indicates in the eCRF his clinical suspicion level of MM and decided action.

The investigator takes images of the lesion(s) again, this time with a mobile phone, containing the IMD AI SW, connected to a dermatoscope, and follows the on-screen instructions, see appendix 13.3. The image is processed by the AI SW and the results are visible on the screen within seconds. A unique auto generated code number is also presented. The code number is registered on the enrollment log and in the eCRF. The investigator records how he considers that the degree of suspicion of MM (higher vs lower) would have been affected by the AI SW result if it had been the governing body for the treatment. When the PAD result is available the outcome is documented in the eCRF.

Figure 1. Investigator workflow for assessing MM suspicion and action to be taken

[figure not shown]

02

AI MEDICAL TECHNOLOGY AIM AB

Document Doc. id. Version Page

Clinical investigation Plan / Investigation code- AI-DSMM/ GR 21- 023 01 24 (52)

Visits and assessments will be performed as described in Table 9.1. Each assessment is further described in Section 9.5.

DocumentDoc. id.VersionPageClinical investigation Plan / Investigation code- AI-DSMM/GR 21- 0230125 (52)

Table 9.1 Schedule of events

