9.3.5 Exclusion criteria

Subjects must not enter the investigation if any of the following exclusion criteria are fulfilled:

- 1. Cutaneous lesions that are considered as benign by the investigator and thus not subject for further clinical investigation
- 2. Cutaneous lesions in areas that are not suitable for dermoscopic imaging
- 3. Cutaneous lesions in areas with any form of scarring of tissue due to injury
- 4. Damaged or injured non intact skin where the cutaneous lesion is located
- 5. Individuals with skin type V and VI according to the Fitzpatrick scale (darker brown or black coloured skin)

Template Doc. id. Version

02

Document	Doc. id.	Version	Page	
Clinical investigation Plan / Investigation code- AI-DSMM/	GR 21- 023	01	28 (52)	

- 6. Cutaneous lesions in areas covered by tattoos
- 7. Cutaneous lesions in abundantly hairy skin areas (provided the area cannot be shaved freely from the hair to allow clear view for the dermatoscope)
- 8. Images where the entire lesion is not inside the photo
- 9. Images that are out of focus

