9.7.4 Analysis of safety

9.7.4.1 Endpoint 1

The main risks identified for similar devices are incorrect diagnosis (false positives and false negatives) due to limitations in the training data set that was used to develop the software. According to the risk management, the only unacceptable risk identified for Dermalytics is that some individuals, including patients with ulcerations (damage to the skin), external modification to the skin, absence of surrounding skin (normal skin around), will be excluded. This is stated in the IFU for

Template Doc. id. Version

CIP Template QMS 12-01- 02
01

Document	Doc. id.	Version	Page	
Clinical investigation Plan / Investigation code- AI-DSMM/	GR 21- 023	01	39 (52)	_

the IMD. The prevalence of incorrect diagnosis will be captured in the primary endpoint analysis, as well as the possibility of reduced risk of missing malignant melanomas (false negatives). The consequences of false negatives will be evaluated by collecting health economic data. To this end, the participating clinicians will be provided a survey with questions on how the use of Dermalytics would affect health economic aspects, such as time to treatment, number of visits to dermatologists and number of excisions.

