9.7.6 Determination of sample size

The general practitioner (GP) will only include subjects in the investigation with lesions where melanoma cannot be ruled out. All lesions where melanoma cannot be ruled out will be sent for an analysis (final classification) to confirm – or not confirm – if the suspected melanoma is a melanoma or not. Each lesion where melanoma cannot be ruled out will be analysed by the IMD and the IMD will classify each lesion where melanoma cannot be ruled out as "Low Risk of being a melanoma" (Low) or "High risk of being a melanoma" (High).

In Table 1 the possible outcomes are described and (A+D)/(A+B+C+D) is the proportion of correct classifications by the IMD.

Template Doc. id. Version

CIP Template QMS 12-01- 02
01

Document Doc. id. Version Page

Clinical investigation Plan / Investigation code- AI-DSMM/ GR 21- 023 01 40 (52)

Table 1 Outcome (m = number of patients) for a binary variable where two groups of observations are linked together.					
			The Al device		
		High	Low	Total	
Final classification	Melanoma	А	В	A+B	
	Not melanoma	С	D	C+D	
	Total	A+C	B+D	A+B+C+D	

The expected value of (A+D)/(A+B+C+D) is denoted π and then the hypotheses of interest are

 H_0 : $\pi \leq \pi_0$

 H_1 : $\pi > \pi_0$

The null-hypothesis (H₀) will be rejected if the one-sided p-value is less than a. If $\pi = \pi_1$ the power to reject H₀ should be β .

Typically, a = 2.5 % and β = 80 % or 90 %. The p-value will be calculated using the exact Binomial test.

In a successful investigation H_0 is rejected and then H_1 is accepted.

Document Doc. id. Version Page

Clinical investigation Plan / Investigation code- AI-DSMM/ GR 21- 023 01 41 (52)

In Table 2 the needed number of lesions is presented based on the formula above and for statistical power 90%.

Table 2	Number of lesions where melanoma cannot be ruled out needed to achieve 80% power to reject (i.e. get a one-sided p-value less than 2.5%) the null-hypothesis by proportions to be rejected (i.e., π_0) and by assumed true proportions (i.e. π_1). Calculated by Sample Size a single proportion V01.xls.					
True Proportion (π ₁)		Р	roportion to b	oe rejected (π	:0)	
(71)	50%	60%	70%	80%	90%	95%
55%	783					
60%	194					
65%	85	742				·
70%	47	182				
75%	29	78	638			
80%	20	43	153			·
85%	14	26	64	471		·
90%	10	17	34	108		
95%	7	11	19	42	239	

Document			Doc. id.	Version	Page	
Clinical investigation Plan / Investigation code- AI-DSMM/		GR 21- 023	3 01	42 (52)		
100%	4	6	9	16	35	73

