The set expectation of 95% true proportion is based on in-silico experiments on a proprietary dataset of images which found a sensitivity of 95.1 \pm 0.6%.

The accuracy of AI decision support will be measured against gold standard (PAD) as well as against experienced dermatologists and general practitioners (average) and verified at: sensitivity> 95%, specificity> 75%, numbers needed to excise (NNE) <7, positive predictive value (PPV))> 15% and negative predictive value (NPV)> 99.5%. The average sensitivity for general practitioners in previous meta-analyzes is estimated at about 81%.

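### Only GP-suspected lesions are enrolled, so the primary analysis cannot show fewer missed melanomas, and nothing in the plan makes the cited 81% GP sensitivity comparable with this sample

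*Combined protocol and SAP*

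**What the plan says.** **Who enters.** Section 9.7.6: "The general practitioner (GP) will only include subjects in the investigation with lesions where melanoma cannot be ruled out". Inclusion criterion 2 (9.3.4) agrees, and exclusion criterion 1 (9.3.5) removes "Cutaneous lesions that are considered as benign by the investigator and thus not subject for further clinical investigation". The suspicion range reaches far down: the synopsis says it "also includes very low suspicion of MM but cannot be completely dismissed".

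**What follows for an enrolled lesion.** Section 9.1 lists three actions: "excision at the primary care centre or referral for excision or referral to a dermatologist for further assessment". Dismissal is not among them. Histopathology (PAD) comes from excised lesions (9.5.3). Section 9.3.2 needs 239 PAD-verified lesions, at least 12 of them melanoma, out of about 500 included.

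**Primary endpoint.** Section 9.7.6, Table 1, cross-classifies device result against PAD. The endpoint is (A+D)/(A+B+C+D).

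**Missed melanomas.** Section 9.7.4.1 says the primary endpoint analysis will capture the frequency of incorrect diagnoses "as well as the possibility of reduced risk of missing malignant melanomas (false negatives").

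**GP benchmark.** Section 9.7.6 says device accuracy will be "measured against gold standard (PAD) as well as against experienced dermatologists and general practitioners (average"), lists the performance targets, and closes with "The average sensitivity for general practitioners in previous meta-analyzes is estimated at about 81" per cent. It gives no threshold, population or reference for that figure.

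**GP comparison within the study.** After describing device accuracy against PAD, the synopsis (Methodology) adds: "The corresponding comparison is performed from the examining investigators' estimated clinical degree of suspicion". Sections 9.1 and 9.4.10 have the investigator record the assessment before the device image is taken. No cut of the suspicion level is stated.

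**The concern.** A melanoma that the GP judged benign is never enrolled, imaged by the device or checked by PAD within the study. Yet the plan speaks of learning about missed melanomas, and it places an external GP sensitivity next to the device's targets.

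Two things are at stake. First, a pivotal pre-market report could state that the primary analysis addressed missed melanomas when that analysis holds no information on GP misses. Second, a device sensitivity estimated only in melanomas the GP already suspected could be set beside 81% as if both had the same denominator.

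**Working it through.** **1. The plan's own figure.** Inputs from 9.7.6, Table 2: π1 = 95%, one-sided α = 2.5%, power 80%, and π0 = 90% (the column that yields 239).

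n = [1.960·√(0.90·0.10) + 0.8416·√(0.95·0.05)]² / (0.05)² = 238.03, rounded up to 239.

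The figure reproduces. By the exact binomial test, H0 is rejected at 225 or more correct out of 239, with α = 0.0162 and power 0.781. The calculation concerns overall accuracy and contains no GP quantity, so the present point leaves it alone.

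**2. GP accuracy at the entry threshold.** Every enrolled lesion is GP-positive. With 12 melanomas and 239 − 12 = 227 non-melanomas:
- GP sensitivity = 12/12 = 100%
- GP specificity = 0/227 = 0%

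Both are fixed by the entry rule. Neither 81% nor any other value could be observed.

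**3. What the primary endpoint can show.** Cells A to D come from the device result and PAD only. Cell B counts melanomas the device calls Low, so device false negatives are visible. No cell holds the GP's judgement or a GP-dismissed lesion. The endpoint therefore cannot show a reduction in missed melanomas relative to GPs.

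**4. What 81% would imply under one reading.** Assume it is GP sensitivity over all melanomas presenting to GPs. The documents do not say so.

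Melanomas never enrolled per 12 enrolled = 12·(1 − g)/g, where g is GP sensitivity:
- g = 0.81: 12·0.19/0.81 = 2.8
- g = 0.70: 5.1
- g = 0.90: 1.3

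Device sensitivity over all presenting melanomas = g·s_e + (1 − g)·s_m. Here s_e is its sensitivity in enrolled melanomas and s_m its sensitivity in GP-dismissed ones. The study never observes s_m. With s_e = 0.95, the level targeted in 9.7.6:

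| g | s_m = 0 | s_m = 1 |
|---|---|---|
| 0.70 | 66.5% | 96.5% |
| 0.81 | 77.0% | 96.0% |
| 0.90 | 85.5% | 95.5% |

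At g = 0.81 the range spans 81%. The device matches 81% only if s_m ≥ (0.81 − 0.81·0.95)/0.19 = 0.21.

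**5. Precision with 12 melanomas.** Even if 81% were transferable, 12 of 12 correct gives a one-sided p of 0.81^12 = 0.080 and an exact 95% interval of 73.5% to 100%. For a paired comparison with the GP at a suspicion cut, the two-sided exact McNemar p with all k discordant pairs in one direction is 2·0.5^k: 0.0625 at k = 5 and 0.031 at k = 6. At least 6 such pairs out of about 12 melanomas would be needed for p < 0.05.

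**The case against.** The other side has several good points.

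- **The enrolled population matches the intended use.** Sections 8.1 and 9.4.2 confine the objective and the device to suspected lesions. This stands. Enrolment needs no change, and an explicit caveat beside the targets only makes a stated scope harder to overlook.
- **81% is neither a hypothesis nor a success criterion.** The primary test is π against π0, and the targets in 9.7.6 are separate figures. This stands. But the same paragraph announces a comparison with the average GP and offers no other GP figure, so readers may well put the two side by side.
- **The denominator behind 81% is unknown.** This stands. A reader might infer that the comparison with 81% necessarily favours the device through selection. The documents do not support that, because they do not say whether the figure counts dismissed melanomas.
- **Graded suspicion is recorded before the device result.** A reader might infer that the device can only lose melanomas the GP had found. That holds only at the entry threshold. A melanoma the GP rated very low and the device called High can be observed, and it is evidence on under-suspicion. It is not evidence on missed melanomas, because low-suspicion lesions are still excised or referred.
- **Section 9.7.4.1 speaks of a possibility.** It promises no effect. It does say the primary analysis will capture that possibility, and the analysis cannot.
- **Section 9.7.3.2 defers further analyses to the SAP.** A suspicion cut may be set there; no separate SAP text is among the documents. No analysis can recover lesions that were never enrolled.

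**Conclusion.** The point holds in a limited form. It follows from the entry rule and the endpoint definition alone that the primary analysis cannot show fewer missed melanomas, and that GP sensitivity and specificity at the entry threshold are 100% and 0% by construction.

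The point about 81% is conditional. If the figure counts melanomas GPs dismissed, it is not comparable with device sensitivity here: about 2.8 melanomas would be unenrolled per 12 enrolled, and 95% sensitivity in enrolled lesions would mean 77% to 96% overall. If it rests on some other population or threshold, those numbers do not apply, but comparability would still have to be shown.

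A reader might go further and conclude that the primary test or the sample size is invalid. Neither is affected.

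**What to change.** 1. **Section 9.7.4.1:** delete the statement that the primary endpoint analysis captures a possible reduction in missed melanomas, or limit it to device false negatives among GP-suspected lesions.
2. **Section 9.7.6:** label 81% as background that is not comparable with this sample. State beside the sensitivity and specificity targets that both are conditional on GP suspicion.
3. **GP comparison planned in the synopsis:** before data lock, fix one cut of the pre-AI suspicion level. Report the paired device-minus-GP difference with a confidence interval, separately in melanoma and non-melanoma lesions. State that with about 12 melanomas the sensitivity difference is descriptive only.

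The cost is protocol and SAP wording plus one analysis of data already collected. The downside is a narrower claim: the study can describe the device among lesions a GP already suspects, and cannot speak to melanomas GPs dismiss.

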9.8 Data Management

The Principal Investigator or other qualified and delegated personnel will report data through Trial Online, a web based electronic Data Capture (EDC) system that manages electronic Case Report Forms (eCRFs). Trial Online is fully compliant with FDA 21 CFR Part 11, ISO-14155 and GDPR.

The Data Manager will write a Data Management Plan (DMP) outlining the data management activities in this investigation. The Sponsor will review and approve the DMP.

Each site personnel will receive a unique login to access the system. Site personnel will be trained before receiving access. All data must be entered in English. Any data to be recorded directly on the eCRFs (to be considered as source data) will be identified at the start of the study. The CRFs should always reflect the latest observations made during the subject's participation in the investigation. Therefore, the CRFs should be completed as soon as possible during or after the subject's visit. All data entries and changes done in the eCRF are captured in an audit trail.

The Principal Investigator must verify that all data entries in the CRFs are accurate and correct by signing the completed CRF. Assessments that are not done or not applicable should be stated in the eCRF. The Data Manager and/or Monitor will check the quality of the data and query the data in the eCRF when needed. Pages cannot be signed before all queries are resolved.

Each subject will receive a pseudonymised subject ID within the database. The code key will be kept separately by the site in a secure manner.

Document	Doc. id.	Version	Page	
Clinical investigation Plan / Investigation code- AI-DSMM/	GR 21- 023	01	43 (52)	

The electronic data retention period is of at least 10 years. Archiving of data is performed according to industry standards such as in PDF format.

10 EMERGENCY PROCEDURES

The Principal Investigator is responsible for ensuring that procedures and expertise are available at the investigational site to handle medical emergencies during the investigation.

For this investigation there are no foreseeable emergency situations since the IMD is a MDSW not in contact with the subjects or users.

11 MANAGEMENT OF THE INVESTIGATION

11.1 CIP Amendments

Any proposed change to the approved Final CIP (including appendices) will be documented in a written and numbered CIP amendment. All amendments including substantial changes to the CIP or to the Subject Information/ICF must be submitted to the appropriate IEC and Competent Authority for approval, according to applicable national regulations.

11.2 Time table

The end of the clinical part of the investigation is defined as the enrolment of approximately 500 lesions where MM could not be ruled out, to reach the target of 239 evaluable (having PAD outcome result) lesions, with 12 positive PAD results. It is estimated that the PAD results will come from the laboratory within approximately 2 months time frame from each excision.

The enrolment period of the investigation is expected to start in Quarter 1, 2022 and to be completed by Quarter 3, 2022.

11.3 Discontinuation of the investigation

The Sponsor reserves the right to discontinue the investigation at any time, but intends only to exercise this right for significant and documented reasons (e.g. valid scientific or administrative reasons, risk to the subjects or non-compliance by the Investigator).

Template Doc. id. Version

CIP Template QMS 12-01- 02

01

Document	Doc. id.	Version	Page	
Clinical investigation Plan / Investigation code- AI-DSMM/	GR 21- 023	01	44 (52)	_

After such a decision all CRFs should be completed as far as possible.

The Sponsor must inform the Competent Authority and IEC concerned as appropriate about any premature termination.

